All participants in this study will be de-identified.

Outcomes

Hospitalisation outcomes of interest will include the following conditions.

Mother	ICD-10-CM
Still birth, preterm birth pregnancy complications	P95 Stillbirth ⁹ O60 Preterm labour Z37 Outcome of delivery 
 • Single stillbirth • Twins, one liveborn and one stillborn • Twins, both stillborn • Other multiple births, all stillborn O00-O99.9 Pregnancy, childbirth and the puerperium
Infant	
Certain conditions originating in the perinatal period	Newborn affected by maternal factors and by complications of pregnancy, labour, and delivery P00-P96
Early neonatal death, SIDS	Ill-defined and unknown causes of mortality R95-R99.9
Congenital anomalies (CVS, CNS, other)	Congenital malformations, deformations and chromosomal abnormalities Q00-Q99.9
Infectious Diseases (pertussis, , etc.)	Certain infectious and parasitic diseases A00-B99
Meningitis	Meningitis due to other and unspecified causes G03 
 •arachnoiditis NOS •leptomeningitis NOS •meningitis NOS •pachymeningitis NOS
Encephalitis	Encephalitis, myelitis and encephalomyelitis G04 
 •acute ascending myelitis •meningoencephalitis •meningomyelitis
Lower respiratory (bronchiolitis, asthma, pneumonia, acute unspecified LRTI, bronchiectasis, Acute bronchitis, lung abscesses/pyothorax	Diseases of the respiratory system J00-J99
Neurological	Diseases of the nervous system G00-G99

⁹ Information about stillbirths is recorded in the Mortality Collection. The Mortality Collection includes extra information about fetal and infant deaths, such as gestation and birth weight. The ICD codes we propose are: P95 Fetal death of unspecified cause Z37 Outcome of delivery, Z37.1Single stillbirth, Z37.3 Twins, one live born one stillborn, Z37.4 Twins, both stillborn, Z37.7 Other multiple births, all stillborn

Pregnancy duration will be classified using the gestational age field from the National Maternity Collection data set. This field gives the duration of pregnancy in number of completed weeks. Preterm will be defined as birth before 37 weeks gestation. Normal term will be defined as birth between 37 and 41 weeks gestation. Post-term will be defined as birth after 41 weeks gestation.

The following codes are available so we can get banded weeks of gestation.

1518 Duration of pregnancy

Code	Number	
O09.0	<5	Completed weeks
O09.1	5-13	Completed weeks

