O09.2	14-19	Completed weeks
O09.3	20-25	Completed weeks
O09.4	26-33	Completed weeks
O09.5	34-36	Completed weeks
O09.9	Unspecified duration of pregnancy	

The yellow highlights are periods outside of the inclusion criteria.

Codes O09 should also have the following codes assigned for additional diagnoses:

Abortion	O00-007	Pregnancy with abortive outcome
Threatened abortion	O20.0	
Fetal death in utero	O36.4	
Premature rupture of membranes	O42	Before 37 completed weeks of gestation
Threatened premature labour	O47.0	False labour Before 37 completed weeks of gestation
Early onset of labour	O60	Early Preterm labour

Example

Patient admitted at 28 weeks gestation with a diagnosis of fetal death in utero (FDIU)

Medical and surgical induction of labour

O36.4	Maternal care for intrauterine death
O60.1	Preterm labour with preterm delivery
O09.4	Duration of pregnancy 26-33 weeks
Z37.1	Single stillbirth

1527- O48 will indicate prolonged pregnancy post dates and post term.

Some women deliver outside the hospital setting and this is estimated by the MoH at around 2%; however, information about these births is available via the National Maternity

Collection. All births, regardless of delivery setting, are assigned a unique National Health Index number. This allows capture of all post-birth hospital and/or notification events for all infants.

Inclusion criteria

Women

NZ women who are pregnant during the study period

Infants

Infants of the women who were pregnant during the study period

Study Two: Prospective intensive monitoring study of safety in pregnant women administered Tdap vaccination

This is a prospective observational study. It will describe any adverse events in pregnant mothers who received Tdap occurring within one month following immunisation. The data for this part of the study will be collected using the same methodology as that currently being used in Canterbury (i.e., Study Three currently in progress) and will therefore be directly comparable and also joint analysis will be possible for the maternal outcomes.

NOTE: We will not have any cases of spontaneous abortion in Studies Two and Three as the lower gestation eligible for vaccination and therefore inclusion in the study is 28 weeks.

Study population

All women vaccinated during pregnancy at any General Practice in NZ with Tdap vaccine will form the Study Two population.

Study participants

Study Two will include women 28–38 weeks pregnant.

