Rates and patterns of adverse events in women who were administered Tdap during pregnancy

Multiple pregnancies

While the number of visits during pregnancy could have an impact on the pregnancy outcome within the study population in Study Two and Three (but not in Study One). The frequency of prenatal care is a potential confounder as it may be associated both with women receiving Tdap or not, and with birth outcomes. There is no way to capture the number of prenatal visits women have from nationally available data. However, the National Maternity Collection does “contain data on primary maternity services provided under Section 88 of the NZ Public Health and Disability Act 2000. This information is sourced from lead maternity carer claims for payment.” This information might be useable as a proxy to indicate frequency of prenatal care.

Study Three: Intensive monitoring study of pregnant women administered Tdap during pregnancy and their infants

Study Three involves extending and supporting the intensive monitoring study currently being conducted in the Canterbury DHB by [name] (Principal Investigator). Briefly this study runs as per Study Two except the women and their infants are followed up intensively for a period of one year after the birth of the infant. The data collected for the period of one month post vaccination in Study Three will be able to be pooled for the overlapping subset of participants also in Study Two.

Study Three includes women receiving the vaccine under the DHB programme at 30–36 weeks in the Canterbury region.

Figure 1. Study population and outcomes

[figure not shown]
[figure not shown]

Figure 2. Monitoring of pregnant women receiving pertussis during pregnancy

Canterbury DHB continues intensive follow up for birth outcomes and infant outcomes for one year for a sample of 300 women and their infants. Infant follow up at three to seven months and 12 months of age in this DHB as per Canterbury protocol (Study Three) (Appendix 8).

Study procedures

Study One (utilising whole population data-linking)

Data sets for hospitalisations, pertussis notifications, infant vaccination and maternal Tdap vaccination will be obtained for the period 1 January 2009 to year ending 2013 from the following national databases:

- National Minimum Dataset for hospitalisation data
- The National Immunisation Register for infant immunisation data
- Notification data from the ESR
- Pregnancy Immunisation records from the HealthPAC claims database

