As specific diagnoses are not necessarily independent events each person will only be counted once for each hospitalisation, the primary diagnosis and repeat admissions for the same episode will be removed, including transfers from one hospital to another.

For diagnosis where individuals may have multiple admissions for different occurrences and the outcome is a count, Poisson regression will be used with testing and adjustment for overdispersion where required.

The temporal relationship between onset of events and vaccination will be presented including distribution where appropriate,

Serious adverse events will be reported as detailed clinical cases.

To analyse the effect of Tdap on still births we will perform a survival analysis. The time dependent explanatory variable of vaccination status and 'failure' of still birth and censored at birth, also including demographics as explanatory variables. The independent explanatory variable will be Tdap vaccination status of the mother (time dependent). Time will commence at the beginning of the inclusion time for an individual— 28(20) weeks gestation. Women will be censored at time of live birth or at the end of the study period, 31 December 2013, whichever occurs first.

Study Two (N=~300)

Estimated number of women receiving pertussis vaccine during pregnancy for study period, potential study population

The birth cohort in NZ is approximately 65,000 per annum. Tdap is funded for pregnant women, but it is difficult to estimate how many women will take up the vaccine. In one DHB with a birth cohort of 6,000 who were first to offer pertussis vaccine free to pregnant women, 220 claims for the Tdap vaccine had been lodged in six weeks and 1,164 over eight months. At the 10th June 2012, out of 255 claims processed at that time 22 (9%) of women had not consented to follow up. The number of women able to be recruited to the Canterbury study is limited by available nurse time.

Based on the experience in Canterbury assuming sufficient workforce capacity the potential number of women available for follow up over a one-year period is:

National birth cohort 65,000

Uptake of pertussis vaccine in pregnancy 10–40%

Potential annual vaccinated cohort 6,500–26,000

Likely to consent (90%) 5,850–23,400

Eligible to participate (87%) 5,090–22,620

- Participation by general practices (success in obtaining informed consent to follow up) estimate 30–90% (likely to be higher rather than lower)

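### Study One's one-count, primary-diagnosis rule conflicts with its code-based outcomes, and the Mortality Collection named for stillbirths is missing from the extraction list

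*Protocol*

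**What the plan says.** **Counting rule.** Protocol, Statistical analysis and sample size justification, Study One, Analysis, gives as its reason that diagnoses are not necessarily independent. It then says "each person will only be counted once for each hospitalisation, the primary diagnosis and repeat admissions for the same episode will be removed", transfers between hospitals included. Poisson regression is planned where one person may have several separate admissions for a diagnosis.

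**Outcomes.** In Study One, Outcomes, the table introduced by "Hospitalisation outcomes of interest will include the following conditions" lists for mothers stillbirth (P95, Z37), preterm labour (O60) and the whole range O00-O99.9. For infants it lists, among others, P00-P96, Q00-Q99.9 and, for early neonatal death and SIDS, R95-R99.9. Footnote 9 spells out the stillbirth definition: "The ICD codes we propose are: P95 Fetal death of unspecified cause Z37 Outcome of delivery", with Z37.1, Z37.3, Z37.4 and Z37.7.

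**Worked example.** The same section shows one admission at 28 weeks for fetal death in utero. It has four codes in this order: O36.4 ("Maternal care for intrauterine death"), O60.1 ("Preterm labour with preterm delivery"), O09.4 (26-33 weeks) and Z37.1 (single stillbirth).

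**Sources.** Footnote 9 states: "Information about stillbirths is recorded in the Mortality Collection". It adds that this collection has extra information on fetal and infant deaths, such as gestation and birth weight. Study procedures, Study One, lists five databases, beginning with "National Minimum Dataset for hospitalisation data" and followed by the National Immunisation Register, ESR notifications, HealthPAC claims and the National Maternity Collection.

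**The concern.** The outcome definitions depend on particular codes, several of which are expected on one admission. A rule that keeps one code per admission cannot populate all of them. The outcomes most exposed are those that tend to accompany another reason for admission: the stillbirth delivery-outcome codes, and infant anomalies or perinatal conditions recorded as additional diagnoses.

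At stake is Study One's lead objective, the background rates for key endpoints in mothers and infants. Missed events make those rates too low and leave fewer events for the exposed-unexposed comparisons. The source gap adds to this. The stillbirth survival model names no source for its events, and a SIDS death outside hospital need not generate a hospital record.

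**Working it through.** The plan states no figure on this point, so none is reproduced. The check applies the counting rule to the protocol's own example and compares the source list with footnote 9.

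**Step 1: which code is primary.** The example does not label one. The reason for admission is fetal death in utero and O36.4 is listed first, so O36.4 is the natural reading. The table shows every alternative.

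| Code(s) kept | Stillbirth (P95/Z37) | Preterm labour (O60) | O00-O99.9 |
|---|---|---|---|
| O36.4 only | 0 | 0 | 1 |
| O60.1 only | 0 | 1 | 1 |
| O09.4 only | 0 | 0 | 1 |
| Z37.1 only | 1 | 0 | 0 |
| Any position, once per outcome | 1 | 1 | 1 |

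On the natural reading 1 of 4 codes survives, and the protocol's own stillbirth example is not counted as a stillbirth. P95, the other stillbirth code, is not on the record. No choice of a single code keeps both the stillbirth and the preterm-labour outcome.

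**Step 2: what is not lost.** Study One, Outcomes, classifies pregnancy duration from the gestational age field of the National Maternity Collection, with preterm birth defined as before 37 weeks. That collection is on the extraction list. The O60 code is at risk; preterm birth as an outcome is not.

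**Step 3: does the independence argument require the rule?** The Analysis section plans logistic regression for specific adverse events. A woman counted once in a stillbirth model and once in a preterm-labour model appears once in each, so no independence assumption within either model is broken. One count per person per outcome prevents double counting without discarding events.

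**Step 4: sources.** Five databases are listed, and the Mortality Collection is not one of them. For infants, Study One, Outcomes, claims capture of hospital and notification events after birth. Neither covers a death outside hospital.

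**Step 5: size.** Let f be the fraction of true events for an outcome that the rule drops. The observed rate is (1 - f) times the true rate. For a rare outcome with the same f in both groups, the standard error of the log odds ratio grows by about 1/sqrt(1 - f). The documents do not give f. As a pure assumption over 0.2 to 0.8:

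- f = 0.2: 1/sqrt(0.8) = 1.12
- f = 0.5: 1/sqrt(0.5) = 1.41
- f = 0.8: 1/sqrt(0.2) = 2.24

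These show how the loss would scale; they do not estimate it. They do not apply to preterm birth, and f need not be the same across outcomes.

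**The case against.** The strongest reply is that the sentence is garbled and should not be read at its harshest. Read literally, it would have the primary diagnosis removed, which cannot be meant. Its evident purpose is to avoid double counting, and the coding section expects additional diagnoses alongside O09, which suggests that secondary codes will be used. That stands as an argument that the sections must be reconciled. It does not remove the conflict, because a data analyst who follows the Analysis section would keep one diagnosis. Rules on diagnosis position can also be left to an analysis plan, but here the protocol has stated one.

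Three further limits also stand. O36.4 is itself an intrauterine-death code, so the admission is still counted under O00-O99.9, and adding O36.4 to the definition would recover some stillbirths. The one-count rule is not expressly applied to the survival model. Hospital records can carry Z37.1, so the model is not without any events.

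A reader might infer that preterm births are lost too, or that the survival model has no gestation data. The documents do not support either, because the National Maternity Collection supplies gestational age. A reader might also infer that the vaccine comparison is biased. Nothing shows that codes are lost at different rates in vaccinated and unvaccinated women. With equal loss and rare outcomes, odds ratios are roughly preserved.

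**Conclusion.** The point holds for coded stillbirth, the O60 code, infant conditions not coded first, and infant deaths outside hospital. In the protocol's example the primary-diagnosis rule yields 0 stillbirths where reading all positions yields 1. The source named in footnote 9 is absent from the extraction list, so the stillbirth model has no stated event source beyond hospital codes. The documents do not say whether the National Maternity Collection records stillbirths.

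The consequence is understated background rates and reduced precision for these outcomes, of a size the documents do not allow one to calculate. The conclusion assumes that the rule means one count under the primary diagnosis and that O36.4 is primary in the example. The second assumption matters little for the conflict itself, since no single code satisfies both outcome definitions.

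**What to change.** 1. Replace the counting sentence. Identify each listed outcome from any diagnosis position and count it once per pregnancy or infant per outcome, or once per episode for the outcomes analysed as counts. Keep the removal of transfers and of repeat admissions for the same episode. Use the primary diagnosis only in tables of reason for admission.
2. State the stillbirth event definition, including whether O36.4 belongs to it, and the data source for the survival model.
3. Add the Mortality Collection to the extraction list, linked by NHI, for stillbirths and infant deaths.

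The cost is a few sentences, one more national dataset request and slightly more linkage work. It should be done before the data request goes out: the Study duration table has the 2009-2013 data arriving at month 12.

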Intensive safety monitoring (Study Three) *Canterbury District Health Board (DHB), [name] (PI)*

To describe adverse events in women who were administered Tdap under the DHB programme between 30–36 weeks of gestation

To describe outcomes of babies whose mothers were vaccinated with Tdap in the Canterbury region during week 30 to 36 of pregnancy (including birth history, weight and head circumference and any congenital abnormalities)

Clinical hypothesis

The rates and patterns of adverse events following administration of Tdap during pregnancy (including the rates and patterns of any adverse pregnancy outcome, and the outcomes in infants up to one year of age), are similar to those where no vaccination during pregnancy occurred.

Background

New Zealand (NZ) is currently experiencing a significant increase in pertussis. The number of notified cases has risen dramatically from July 2011 and remained high throughout 2012. Increases in pertussis notifications have been seen previously and occur over a four- to five-year cycle in NZ. The underlying reasons for such a cycle are unknown.

Notification data and associated rates by age indicate that the under-one-year-olds are the most vulnerable with a cumulative notification rate in 2012 of 606 per 100,000 or 378 cases, 167 being hospitalised. This is the highest cumulative notification rate of any age group in 2012. There were 40 notifications of infants under six weeks old, 36 of which were hospitalised.

In 2012 (up to 23 November) 287 hospitalisations were reported. Of these, 167 (58.2%) were infants under one year old. Two deaths were reported, one in a three-year-old unimmunised child with underlying health conditions, and one in an infant aged less than six weeks with a history of preterm birth. All infants hospitalised with pertussis infection younger than six weeks of age have not received their first pertussis immunisation. Data in NZ shows about 20% of infant cases are infected by their mothers.¹

The most recent data for the two surveillance weeks (24 November–7 December 2012) showed 248 new cases of pertussis (113 and 135 cases, respectively) notified, including 111 confirmed cases, 92 probable cases, 14 suspect cases, and 31 cases still under investigation. Twenty-nine (11.7%) of the notified cases were aged less than one year. Fourteen cases were hospitalised.

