- Estimated minimum and maximum number of women for follow up of pertussis vaccine 1,527–20,358

Sample size and power

As this is an observational study we plan to describe the confidence intervals for the proportions of AEs. With a sample of 300 vaccinated participants, if event occurs in 10% of the group the 95% CI would be 7–14%; if 5%, 2.8–8.1%; if 1%, 0.2–2.9%. Additional power will be achieved by combining the data from the Canterbury study (Study Three), which aims to include 300 women vaccinated with Tdap.

Statistical Analyses

The pregnancy safety data will be descriptive in nature, including percentages and 95% confidence intervals. The rates of AEs and SAEs following pertussis vaccine will be discussed in context with the rates previously described for pertussis. The expected background rates of MAEs and SAEs for Tdap given during pregnancy are unknown, but as a guide the rates of MAEs for pregnant women receiving influenza vaccine previously reported ranged from 1.1 to 3.8% while the rate of SAEs ranged from 0.4 to 1.5%.

Women who have complicated pregnancies will be excluded from the final analyses and described separately.

The temporal relationship between onset of events and vaccination will be presented including distribution where appropriate.

Serious adverse events will be reported as detailed clinical cases. Other events will be groups according to Brighton Collaboration Definitions.

Study Three (N=~300)

From the protocol for Canterbury DHB (Appendix 8): Principal Investigator, [name].

As this study is an observational study, the pregnancy outcomes and safety data will be descriptive in nature. The rates of AEs and SAEs will be compared to published background rates for the general population. The expected rates of MAEs and SAEs for Tdap given during pregnancy is unknown, but as a guide the rates of MAEs for pregnant women receiving influenza vaccine in this paper ranged from 1.1 to 3.8% while the rate of SAEs ranged from 0.4 to 1.5%. Where the known background incidence of 0.01 for a particular adverse event, a sample size of 300 achieves 80% power to detect an additional incidence rate of 0.0175 when the significance level is 0.05.

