It is anticipated that the difference in AEs between subgroups in the trial will be small. As this is an observational study we therefore plan to describe the confidence intervals for the proportions of AEs within each group. A sample size of 300 produces a two-sided 95% confidence interval with a width equal to 0.081 when the sample proportion is 0.150.

Women who have multiple pregnancies and/or complicated pregnancies will be excluded from the final analyses and described separately.

Total expected participants

	Study population	Sample size	
--	------------------	-------------	--

Study One	325,000		Total pertussis-vaccinated maternal population
Study Two	1,527–20,358	300	~300 pertussis vaccinees
Study Three	6,000	300	300 pertussis vaccinees

Vaccines

Pertussis vaccine

The pertussis vaccine funded for pregnant women is Boostrix[®]. There are other licensed vaccines but no other pertussis vaccines currently funded for pregnant women in NZ.

Specific vaccine supply requirement

N/A. This is an observational study. There are no vaccine requirements for this study.

Adverse experience reporting

Adverse Event data are being accessed/collected during this project in Study Two and Three.

The Investigator will report SAEs (either initial or follow-up reports) to:

The NZ Centre for Adverse Reaction Monitoring (CARM) at the University of Otago according to local requirements. (See Appendix 9, contract Exhibit D, CARM Reporting Form)

The Ethics Committee according to requirements

The Marketing Authorisation Holder within 24 hours according to contracted safety reporting requirements defined in the study contract. Case reporting will include the relevant variables in the GSK “with intensity GCSP reporting form”. (See Appendix 10)

Administration during pregnancy is relevant in the age group, so pregnancy reporting is expected to be relevant. All participants will be pregnant.

There will be no causality assessments conducted during this study as this is observational and there is no intervention.

Any adverse events that are reported to the NZ Centre for Adverse Reaction Monitoring (CARM) undergo causality assessment. This data is provided to the WHO and the MoH.

CARM is the official regulatory body in charge of receiving all adverse event reports in NZ. CARM collaborates with and pools anonymised data, together with other national monitoring centres, into the database of the World Health Organization's International Drug Monitoring Programme.

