Appendix 7: Study Two Phone Survey 2 (4-weeks post vaccine)

PIPS Patient Participant Phone Survey (4 weeks post vaccine)

Researcher: _____ **Date:** _____

The following questions ask about your memory of events for the period up to 4 weeks following when you received the Tdap vaccine (whooping cough vaccine).

	Yes	No	Date started	Date resolved/ recovered	Resolving/ recovering	Not resolved/ recovered	Resolved/ recovered with lasting effects
1. Have you experienced any adverse events/symptoms within the one month post vaccination?							
2. Since receiving the vaccine, have you had any infections such as a: urine, ear, nose, throat, lung infection, gastroenteritis, skin infections							
3. Since receiving the vaccine, have you experienced any of the following:							
Muscle aches and pains							
New onset high blood pressure							
Severe nausea or vomiting							

Pertussis in Pregnancy Safety (PIPS) Study Protocol
 Confidential
 Not for Public Circulation or Reproduction

Premature labour							
Premature rupture of membranes							
Severe abdominal pain							
Vaginal bleeding							
Depression or psychological disorders							
Unexplained itching of the skin							
Spontaneous abortion or threatened abortion							
4. Since receiving the vaccine, have you needed to see a doctor for any of the events described above or for any other reason?		If no, go to end.	If yes, please indicate where you saw the doctor:  Emergency Room/After Hours  Hospital  GP Practice				
4b. What was the diagnosis?							
4c. If there was no diagnosis, what were the signs and symptoms?							

4d. Can we contact your family doctor for further details?
(If yes, please provide Dr name and hospital/practice details)

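### Studies Two and Three exclude women with complicated pregnancies from the final analyses without limiting this to complications that preceded vaccination, so a solicited adverse event can itself cause exclusion

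*Protocol*

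**What the plan says.** The exclusion appears in three places in the protocol. The Statistical Analyses text for Study Two reads: "Women who have complicated pregnancies will be excluded from the final analyses and described separately". The statistical text for Study Three, and the Statistical Analysis section of the Canterbury protocol (Appendix 8) from which it comes, read: "Women who have multiple pregnancies and/or complicated pregnancies will be excluded from the final analyses and described separately". A complicated pregnancy is not defined in any of them, and none places the complication before or after vaccination. It is not an enrolment exclusion in either study, so the rule acts only at analysis.

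The aims are wider than this. The clinical hypothesis covers adverse events after Tdap, "including the rates and patterns of any adverse pregnancy outcome". The Study Two design says: "It will describe any adverse events in pregnant mothers who received Tdap occurring within one month following immunisation". Its endpoint is "Rates and patterns of adverse events in women who were administered Tdap during pregnancy". The first Study Three objective is "To describe adverse events in women who were administered Tdap under the DHB programme between 30–36 weeks of gestation". None of these is restricted to uncomplicated pregnancies.

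The four-week phone survey (Appendix 7) solicits, among other events, "New onset high blood pressure" and "Premature rupture of membranes", together with premature labour, vaginal bleeding and severe abdominal pain. The four-week written questionnaire in the Canterbury protocol lists the same events.

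**The concern.** Several of the solicited events are complications of pregnancy in ordinary usage. A woman who develops one in the month after vaccination has had an event the study set out to count. Under the rule as worded she may also be classed as having a complicated pregnancy and leave both the numerator and the denominator. That is selection on the outcome, and its direction is known: the reported proportion of such events can only fall.

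The AE and SAE percentages with their 95% confidence intervals are the main statistical output of these two descriptive studies. Study Three also compares its rates with published general-population background rates. Nothing in the text limits those background rates to uncomplicated pregnancies. A cohort from which women with complications have been removed would compare favourably even if the vaccine had no effect.

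**Working it through.** **Reproducing the plan's figures.** Study Two gives 95% intervals for 300 women: 7–14% at 10%, 2.8–8.1% at 5% and 0.2–2.9% at 1%. Exact (Clopper-Pearson) intervals for 30, 15 and 3 events in 300 are 6.9–14.0%, 2.8–8.1% and 0.2–2.9%. They match, and all of them assume that the full 300 are analysed.

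**Effect of the rule.** Let c be the true proportion with a post-vaccination complication and f the share of those women who are classed as complicated and excluded.

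- Events left: 300c(1 − f)
- Women left: 300(1 − cf)
- Expected reported rate: c(1 − f) / (1 − cf)

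The protocol gives neither c nor f. Both are assumptions: c is taken at the protocol's own three illustrative rates, and f runs over its whole range.

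| Assumed true rate | None excluded (f = 0) | Half excluded (f = 0.5) | All excluded (f = 1) |
|---|---|---|---|
| 1% | 3/300 = 1.0% (0.2–2.9%) | 1.5/298.5 = 0.5% | 0/297 (upper limit 1.2%) |
| 5% | 15/300 = 5.0% (2.8–8.1%) | 7.5/292.5 = 2.6% | 0/285 (upper limit 1.3%) |
| 10% | 30/300 = 10.0% (6.9–14.0%) | 15/285 = 5.3% (3.0–8.5%) | 0/270 (upper limit 1.4%) |

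Fractional counts are expected values. With zero events the exact upper limit is 1 − 0.025^(1/n); for n = 285 this is 1 − 0.025^(1/285) = 1.3%. At a true rate of 5% with all such women excluded, and at 10% with half or all excluded, the reported interval does not contain the true rate. At 1% with all excluded it still does, because the interval is wide relative to the rate.

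**SAEs.** The protocol's guide rate of 0.4–1.5%, taken from influenza vaccination in pregnancy, is 300 × 0.004 = 1.2 to 300 × 0.015 = 4.5 women. Hospitalisation makes an event serious under the protocol's definition, so a complication that leads to admission is an SAE. Excluding one or two such women could remove a large part of the SAE proportion.

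**Precision.** If 10–20% of women were excluded (assumed), 270 to 240 would remain. The exact interval at 10% would be 6.7–14.2% or 6.5–14.5%, against 6.9–14.0% with all 300. The loss of precision is small; the problem is bias.

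**The case against.** The best defence is that the term means a risk status already present at vaccination. Study Three pairs it with multiple pregnancy, which is normally settled by 28 weeks, and no text links the solicited events to the exclusion. A separate analysis plan might also define the term. This reading is possible and would remove the bias described here, but the protocol does not state it. The point is more than a missing definition: the protocol fixes an exclusion that, as worded, conflicts with its own endpoint.

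Second, the events do not disappear. The excluded women are described separately, SAEs are reported as detailed cases, and stillbirth, fetal death and similar outcomes are reported within 24 hours. It would be wrong to infer that complications would be hidden. Nevertheless, descriptions and case reports do not restore the planned percentages, their intervals or the Study Three comparison.

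Third, much of what these studies count is local reactions, fever and other systemic symptoms, which are far less affected. Study One compares pregnancy complications in vaccinated and unvaccinated women and has no such exclusion. Both facts narrow the point to complication-type AEs and SAEs in Studies Two and Three.

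Fourth, a reader might infer that infants of excluded women also leave the Study Three birth and anomaly results. The rule names only women, so that removal is not stated. The protocol leaves the infants' position open.

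Finally, the background rates come from a cited source that is not available here. That they include complicated pregnancies is inferred from their description as general-population rates. Study Two has no such formal comparison.

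**Conclusion.** The concern holds in this form: the rule as written permits exclusion because of a solicited outcome and, where that happens, biases pregnancy-complication AE and SAE proportions towards safety. The direction is certain, but the size is not. At an assumed true rate of 5%, the expected reported rate runs from 5.0% through about 2.6% to zero as the share of affected women classed as complicated goes from none to half to all. The zero result, with its upper limit of 1.3%, is the extreme of an assumed range and not a prediction. The calculation considers only exclusions caused by the event itself. Exclusions for conditions present before vaccination would come on top, and the documents give no frequency for them.

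**What to change.** Replace the sentence in all three places. Keep every enrolled vaccinated woman in the main AE and SAE analysis of Studies Two and Three. State that in Study Three her infant or infants stay in the infant outcome descriptions. Define a complicated pregnancy from complications documented before vaccination, and use that, together with multiple pregnancy, only for a stratified or sensitivity analysis.

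The cost is a few sentences and one additional table. The limitation is the stratifier. Question 6 of the Study Two Referral Form (Appendix 3) and the corresponding Canterbury practice item ask about underlying health conditions. They do not ask specifically about complications of the current pregnancy, and the Referral Form has no item on multiple pregnancy. The definition would therefore have to rest on what was recorded at vaccination or in the GP record, and may be incomplete. The main analysis does not depend on it.
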